8.4 Data Analysis Conventions

Final data analysis will be performed by SDC after the study is completed and the database has been locked and released for unmasking. Statistical programming and analyses will be performed using SAS[®] version 9.4 or higher. Output will be provided in rich text format (RTF) for tables and portable document format (PDF) for tables, listings, and figures using landscape orientation. All study data will be listed by subject, treatment, and visit (as applicable) based on all randomized subjects unless otherwise specified.

Summaries for continuous and ordinal variables will include the number of observations (n), arithmetic mean, standard deviation (SD), median, minimum, and maximum. Minima and maxima will be reported with the same precision as the raw values; means and medians will be presented to one additional decimal place than reported in the raw values. Standard deviations will be presented to two additional decimal places than reported in the raw values. Summaries for discrete variables will include counts and percentages. All percentages will be rounded to one decimal place (i.e., XX.X%). Differences between active treatment groups and placebo will be calculated as active minus placebo and change from baseline will be calculated as follow-up visit minus baseline.

All statistical tests will be two-sided with a significance level of 0.05 (α = 0.05) unless otherwise specified. Confidence intervals (CIs) for differences between treatment groups will be two-sided at 95% confidence. All p-values will be rounded to 4 decimal places; p-values less than 0.0001 will be presented as "<0.0001"; p-values greater than 0.9999 will be presented as ">0.9999."

Unless otherwise specified, summaries will be presented by treatment group and, where appropriate, visit. Listings will be sorted by treatment group, subject number, visit/time point, and parameter as applicable.

Unscheduled visits will not be included in summaries presented by visit (i.e. unscheduled visits will not be mapped to the nearest scheduled visit window and will not be included in the by-visit summaries). Early termination visits will be summarized together with Visit 9 (Day 30; Study Exit). Scheduled visits that are outside of the corresponding visit window will still be included in the applicable summary; however, such instances may be deemed to be a major protocol deviation resulting in an exclusion from the Per-Protocol population analyses. Listings will include data collected at all visits, including unscheduled visits.

8.5 Adjustments for Multiplicity

All six sets of hypotheses described in Section 2.5 will be tested in a hierarchical order, testing the primary hypotheses first (corresponding to Visit 6b), and then proceeding with the key secondary efficacy hypotheses in the order presented below.

- 1. Visit 6b
- 2. Visit 6a
- 3. Visit 5
- 4. Visit 8b
- 5. Visit 8a
- 6. Visit 7

If at any point in the hierarchical order, statistical significance is not demonstrated, testing will stop, and the remaining tests will be deemed not statistically significant.

There will be no adjustment necessary for testing multiple time points within a visit, as statistical significance at all three post-CAC time points is required for a visit to be deemed statistically significant.

9. Disposition of Subjects

Analysis populations, study completion, and withdrawal from the study will be summarized for the ITT population. The summary table will include the numbers of subjects randomized and included in the analysis populations by randomized treatment group for the ITT population and by actual treatment group for the PP and Safety populations. The summary table will also include the numbers of subjects who completed the study. The reasons for withdrawal will be summarized for the applicable subjects. Reasons for withdrawal will include AE, protocol deviation, lost to follow-up, consent withdrawn, Sponsor termination of study, Investigator decision, unsuccessful insertion, other.

Disposition data for all subjects in the ITT population will be presented in a listing. Protocol deviations for the ITT population will also be presented in a listing.

9.1 Demographic Variables

Subject demographic characteristics (age, sex, ethnicity, race, and iris color) will be summarized and presented by treatment group. These summaries will be based on the ITT population. Percentages will be based on the total number of subjects in each treatment group except for iris color, which will be based on the total number of eyes in each treatment group.

Age will be reported in years and calculated using the following formula:

Age = (Informed Consent Date – Date of Birth) / 365.25, truncated as an integer

A subject listing that includes all demographic variables will be provided.

9.2 Pretreatment Variables

At Visit 1 (Day -45) a diagnostic test for allergic disease (skin test) will be performed on subjects without a documented skin test within the past 24 months and the pre- and post-dilation punctum size of each eye will also be assessed. Results from both assessments will be presented in subject listings.

10. Medical History and Concomitant Medications

10.1 Medical History

Medical history will be coded using Medical Dictionary for Regulatory Activities (MedDRA), version 20.0.

Non-ocular medical history will be summarized for the ITT population using discrete summary statistics and presented by treatment group at the subject level by System Organ Class (SOC) and Preferred Term (PT). Ocular medical history will be similarly summarized at the subject level. If a subject reports the same PT multiple times within the same SOC, that PT will only be reported once within that SOC. As with the PT, if a subject reports multiple conditions within the same SOC, that SOC will only be reported once. Percentages will be based on the number of subjects in each treatment group. In the summary, SOC will be listed in order of descending frequency for all subjects; PTs will be listed in order of descending frequency for all subjects; PTs will be listed in order of descending frequency.

Listings of medical history will be generated separately for ocular and non-ocular data.

10.2 Prior and Concomitant Medications

A concomitant medication is any drug or substance administered from Visit 1 (Day -45) through the last study visit, Visit 9 (Day 30). A prior medication is any drug or substance administered prior to Visit 1 (Day - 45). The generic name of the drug or substance, the dose, the route of administration, the duration of treatment (including the start and stop dates), the frequency, the indication, and whether or not the medication was taken due to an AE will be recorded for each drug or substance.

Prior and concomitant medications will be coded using World Health Organization (WHO) Drug Dictionary (Enhanced B2, March 2017) and summarized to the therapeutic drug class (ATC 4 classification) and preferred name. If the ATC 4 classification is not provided, then the next lowest classification that is provided in the coding dictionary will be used. The preferred name will be defined as the active ingredient; if the active ingredient is not provided or includes more than two ingredients (e.g., multivitamins), then the drug name will be summarized as the preferred name.

Prior and concomitant medications will be summarized for the ITT population using discrete summary statistics and presented by treatment group, separated out by ocular and non-ocular medications. Percentages will be based on the number of subjects in each treatment group. Subjects may have more than one medication per ATC text. At each level of subject summarization, a subject will be counted once if he/she reports one or more medications. In the summary, ATC classification will be listed in order of descending frequency for all subjects; preferred name will be listed in order of descending frequency for all subjects.

Listings of prior and concomitant medications will be generated separately for ocular and non-ocular data.

11. Study Therapy Variables

Punctum size (pre- and post-dilation) and exposure to IP will be summarized using quantitative descriptive statistics. A subject will be considered exposed to study drug as long as at least one eye has a successful insertion. Exposure to IP will be calculated as: End Date – Date of Insertion + 1, where the end date is defined as the earliest date at which the insert is not visible in both eyes, the insert is removed from both eyes, or study exit date.

Ease of punctum insertion (easy/moderate/difficult), visualization (easy/moderate/difficult), and removal (minimal, moderate, extensive manipulation) will be presented in subject listings and summarized using counts and percentages. Percentages will be based on the total number of subjects in treatment group for the Safety population.

Punctum size, punctum insertion, visualization, and removal will all be presented in separate listings using the ITT population. Procedural exclusion criteria related to the punctum assessments will be presented in the same listing as study inclusion and exclusion criteria.

Data related to the CAC procedure (CAC time, qualifying allergen and dose) will be presented in a listing.

12. Efficacy Analyses

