#### 7.8. Early Loss of Insert and Patient Follow-up

If at any point post-insertion, the subject is experiencing discomfort or an undesirable reaction due to OTX-DP or PV, it may be removed per the instructions in Appendix H, and the subject should be exited (discontinued) at that time.

If only 1 insert is present at any visit prior to a subject's Exit Visit (Visit 9), that subject should continue in the study for safety. These subjects will not undergo the conjunctival allergen challenge and will therefore return for Visit 9. At this visit, the following procedures will be performed:

- Update of Medical/Medication History
- Assessment of Adverse Events
- Best Corrected Visual Acuity (BCVA) using an ETDRS chart
- Slit Lamp Examination, including punctum exam
- Visualization of OTX-DP or PV
- **IOP Measurement**
- Dilated Fundoscopy Examination

Intracanalicular inserts that are no longer present or removed at any point in the study will not be replaced.

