# 8.13. Visit 9 (Day 30+3): Study Exit

- *Update of Medical/Medication History*
- Adverse Event Query
- Urine Pregnancy Test: This will be given to all women of childbearing potential. See Appendix B.
- Best Corrected Visual Acuity (BCVA) using an ETDRS chart. See Appendix C.
- Slit Lamp Biomicroscopy including punctum exam. See Appendix D.
- Visualization of Intracanalicular Inserts. See Appendix G.
- *IOP Measurement*. See Appendix E.
- Dilated Fundoscopy. See Appendix F.
- Intracanalicular Inserts Removal: If the intracanalicular inserts are still present at this visit, and the subject is experiencing any symptoms related to the inserts, the Investigator will remove the insert(s) according to the procedures outlined in Appendix H. Asymptomatic subjects may leave the office at the completion of visit assessments without removal of inserts.
- Relief Drop Instillation: Subjects may receive a dose of a currently marketed, topical ophthalmic anti-allergic agent (i.e., anti-histamine/vasoconstrictor combination products like Visine®-A®) as they leave the office to relieve any immediate discomfort caused by the allergic reaction.
- Study Exit

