¹⁰ If the inserts are still present, and the subject is experiencing symptoms related to the inserts, the Investigator will remove them according to the removal procedures. Inserts do not need to be removed for asymptomatic subjects.

4. Study Treatments

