4.2 Masking and Unmasking

In the case of a medical emergency or occurrence of a serious adverse event (SAE), the randomization code may be unmasked and made available to the Investigator, Sponsor, and/or other study personnel involved in the conduct of the study. In the absence of medical need, the randomization code will not be available to the above individuals until after the study is completed and the database is locked.

In the event of a medical need, the Investigator will treat each subject, as medically required. If the Investigator feels it is necessary to unmask a subject's treatment assignment after an emergency situation, the Investigator may call the Medical Monitor and notify the Sponsor. The treatment assignment will be revealed on a subject-by-subject basis with the approval of the Medical Monitor and Sponsor, leaving the masking of the remaining subjects intact.

The site will receive one emergency unmasking envelope for every product received and the envelopes should be stored in a secured location. The envelopes and product will both be labeled with the same randomization number. The envelopes are sealed and contain the unmasked treatment information for the corresponding study product.

Ocular Therapeutix will make the final determination if the unmasking request will be granted. Once the unmasking request is granted the Investigator or designee should identify and retrieve the emergency unmasking envelope for the given subject. The emergency unmasking envelope should be opened by the designated site personnel. The Investigator must also indicate in source documents and in the electronic case report form (eCRF) that the mask was broken and provide the date, time, and reason for breaking the mask. Any AE or SAE associated with breaking the mask must be recorded and reported as specified in this protocol.

Subjects will have the investigational product (IP) removed immediately if treatment assignment is unmasked.

5. Sample Size and Power Considerations

Approximately 80 subjects will be randomized at Visit 4b in a 1:1 ratio across the two treatment arms (40 OTX-DP; 40 PV). Up to approximately 10 additional subjects may be enrolled to make up for any subjects who did not complete Visit 6b CAC procedures.

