7.3 Safety

The Safety population includes all randomized subjects who received the IP. The Safety population will be analyzed as treated and will be used for the safety analyses. No data will be excluded for any reason.

8. General Statistical Considerations

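### Ease-of-removal and later ease-of-visualization percentages divide by all Safety subjects, so each grade mixes how often the procedure happened with how difficult it was

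*SAP*

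**What the plan says.** SAP section 11 (Study Therapy Variables) grades insertion and visualization as easy, moderate or difficult, and adds a third scale: "removal (minimal, moderate, extensive manipulation) will be presented in subject listings and summarized using counts and percentages". The next sentence fixes the denominator for all of these: "Percentages will be based on the total number of subjects in treatment group for the Safety population". The outputs are Table 14.1.5.1 (insertion and removal) and Table 14.1.5.2 (visualization), with Listings 16.2.5.1 to 16.2.5.3 behind them.

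The denominator population is broad. SAP section 7.3: "The Safety population includes all randomized subjects who received the IP". Its planned size comes from SAP section 5: "Approximately 80 subjects will be randomized at Visit 4b in a 1:1 ratio across the two treatment arms (40 OTX-DP; 40 PV").

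Removal is not done in everyone. Protocol section 8.13 limits it at Visit 9 to inserts still present in subjects with insert-related symptoms, and adds: "Asymptomatic subjects may leave the office at the completion of visit assessments without removal of inserts". Footnote 10 to the SAP schedule (section 3.2) agrees: "Inserts do not need to be removed for asymptomatic subjects". Before Visit 9, Protocol section 7.8 allows removal if "the subject is experiencing discomfort or an undesirable reaction due to OTX-DP or PV, it may be removed", and Protocol section 9.9.2 calls for removal on unmasking.

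**The concern.** A subject who had no removal has no removal grade, but under the section 11 rule still counts in the denominator. The percentage shown for extensive manipulation is then a product of two things: the fraction of subjects who had a removal, and the fraction of those removals that were extensive. A reader of Table 14.1.5.1 would naturally take it as the second.

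The same applies to visualization at later visits. Inserts are designed to resorb, can be lost and are not replaced. Under Protocol section 7.8, a subject found with only one insert has no further challenges and goes on to Visit 9. Such subjects may have nothing to grade at the visits in between, yet remain in the denominator.

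The comparison between arms is affected too. If the arms differ in how many subjects have a removal, the planned percentages differ even when removal is equally difficult in both.

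**Working it through.** The plan states no expected number of removals and no expected grade distribution, so there is no figure of its own to reproduce.

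**Inputs**
- N = 40 Safety subjects per arm: the planned arm size in SAP section 5, taken as the Safety count.
- R = subjects per arm with a removal: not in the documents. Assumed range 2 to 20.
- k = removals graded extensive. Assumed to be half of R, for illustration.

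**Formulas**
- Percentage as planned = k / N
- Percentage among subjects with a removal = k / R
- Dilution = (k / R) ÷ (k / N) = N / R, which does not depend on k

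**Results at N = 40**

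| R (assumed) | k | As planned, k/40 | Among removals, k/R | Dilution, 40/R |
|---|---|---|---|---|
| 2 | 1 | 2.5% | 50% | 20 |
| 4 | 2 | 5.0% | 50% | 10 |
| 8 | 4 | 10.0% | 50% | 5 |
| 20 | 10 | 25.0% | 50% | 2 |

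The direction is the same for every R below N. The dilution vanishes only if all 40 subjects have a removal.

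**Arm comparison.** Suppose 4 subjects have a removal in one arm and 8 in the other, with half extensive in each. The planned table shows 2/40 = 5% against 4/40 = 10%. Among removals it is 2/4 = 50% against 4/8 = 50%. The apparent twofold difference is a difference in how often removal occurred.

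**Visualization.** If m subjects have an insert examined at a visit, the same algebra gives a dilution of N / m for each grade. The documents give no m.

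**Insertion.** Every Safety subject received an insert, so the denominator is close to complete and dilution is not the issue. What section 11 leaves open is how two eyes become one subject-level grade.

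**Other parts of the SAP.** Sections 13.3 (slit lamp) and 13.5 (fundoscopy) summarize each eye at each visit and divide by subjects who have a result. Section 8.1 makes the eye the unit for safety variables. Section 9.1 names an eye denominator for iris color ("which will be based on the total number of eyes in each treatment group"). Iris color is a fixed trait, so this last comparison shows only that the SAP can state an eye unit when it intends one. Section 11 follows none of these rules and gives no reason.

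**The case against.** The strongest reply is that nothing is hidden. Counts are planned beside the percentages and removals are listed by subject. If every removal is graded, the three counts add up to the number of removals, so 2 of 4 can be read from the same table. This stands: the defect lies in the percentage read alone.

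Second, the Safety count is a valid denominator for another question, namely what fraction of treated subjects had a difficult removal. Subjects with a removal are selected after randomization, and with few of them a comparison between arms is unstable. This also stands, and is why the Safety-based figure should be kept as its own row.

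Four stronger readings are tempting and are not supported:
- That the understatement is tenfold. That is only the R = 4 row; the documents give no removal count. Nor do they say that few inserts will be removed, although the removal rules suggest that not all will be.
- That percentages would sum to 200% because two eyes are pooled over one subject. Section 11 does not describe pooling, and sections 13.3 and 13.5 lay results out by eye.
- That the ease grade is recorded per insert at every visit. Protocol Appendix G schedules a check of insert presence at eight visits; it does not say the ease grade is taken each time.
- That the listed risk of being unable to remove an insert would be understated. The three-grade scale has no category for failed removal, so no change of denominator would reveal it. An untoward event from removal would be expected to appear through adverse event recording.

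**Conclusion.** The point holds for removal, and for visualization at visits where some subjects have no insert to examine. The stated denominator dilutes each grade's share by N/R for removal: 20-fold to 2-fold at N = 40 and R from 2 to 20. The direction follows from the documents for any R below N; the size rests on an assumed R. For insertion only the eye unit needs stating.

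The consequence is descriptive. SAP section 13 plans no inferential testing of safety variables, and no efficacy analysis uses these grades. This is a free improvement, not a flaw that threatens a conclusion of the trial.

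One related inconsistency affects how many removals there will be. Protocol section 5 describes Visit 9 removal of inserts still present without the symptom condition that Protocol section 8.13 and SAP section 3.1 attach. These passages must be reconciled.

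**What to change.** Replace the denominator sentence in SAP section 11 and adjust the shells of Tables 14.1.5.1 and 14.1.5.2:
- Present results by eye, and by visit for visualization.
- Use as denominator the subjects or eyes with a graded assessment: insertion attempted, insert examined at that visit, removal attempted.
- Keep a separate row for the number of subjects with a removal out of all Safety subjects, so that frequency and difficulty can each be read directly.
- State the visits at which the ease-of-visualization grade is recorded.

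The cost is a few lines of SAP text and two table shells, settled before unmasking. The plan gives no sign that new data collection would be needed.

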12.1 Primary Analysis

The primary efficacy variable is ocular itching evaluated by the subject at $3(\pm 1)$, $5(\pm 1)$, and $7(\pm 1)$ minutes post-CAC at Visit 6b (Day 8; 8 hours from Visit 6a). Ocular itching will be evaluated using the following Ora CalibraTM CAC Ocular Itching Scale as defined in Appendix A.

The average of each subject's eyes' itching score at each post-CAC time point will be used as the unit of analysis for ocular itching.

The primary analysis of ocular itching will be performed on the ITT population with MCMC multiple imputation methodology for missing data using an ANCOVA model for each post-CAC time point at Visit 6b, with the time appropriate post-CAC itching scores at Visit 4a as a covariate and treatment group as the sole factor.

For multiple imputations using MCMC, twenty "complete" (imputed) datasets will be produced and analyzed. Results from the analyses on the twenty "complete" datasets will be combined for presentation using SAS PROC MIANALYZE.

A separate imputation model will be fit for each visit and time point. The imputation model will include variables for treatment, baseline measure (the time appropriate post-CAC scores at Visit 4a), and response measure.

The following SAS code will be used to produce twenty "complete" datasets:

```
PROC MI DATA = INDATA SEED = 59411 NIMPUTE = 20 OUT =
OUTDATA1 MINIMUM=. 0 0 MAXIMUM=. 4 4 ROUND =. 0.25 0.25;
BY VISIT TIME;
MCMC INITIAL = EM;
VAR TREATMENT BASELINE SCORE;
RUN;
```

where

- INDATA is the name of the input dataset;
- OUTDATA1 is the name of the output dataset;
- TREATMENT is the name of the treatment group variable in numeric format;
- BASELINE is the time appropriate post-CAC scores at Visit 4a; and
- SCORE is the average (of right eye [OD] and left eye [OS] for each subject) ocular itching score.

After obtaining twenty "complete" datasets, the following SAS code will be employed to run the analysis of covariance (ANCOVA) models by time point on each dataset:

```
ODS OUTPUT SOLUTIONF = MIXPARMS LSMEANS = LS DIFFS = DIFF;
PROC MIXED DATA = OUTDATA1;
BY VISIT TIME _IMPUTATION_;
CLASS TREATMENT;
MODEL SCORE = BASELINE TREATMENT / SOLUTION;
LSMEANS TREATMENT / PDIFF CL;
RUN;
```

where

- *SUBJID* is the subject ID number;

- BASELINE is the time appropriate post-CAC scores at Visit 4a;
- VISIT is the visit; and
- *TIME* is the time point.

The following SAS code will then be used to combine results across imputations for the treatment means and differences respectively:

```
ODS OUTPUT PARAMETERESTIMATES = PE1;
PROC MIANALYZE DATA = LS;
BY VISIT TIME TREATMENT;
MODELEFFECTS ESTIMATE;
STDERR STDERR;
RUN;
ODS OUTPUT PARAMETERESTIMATES = PE2;
PROC MIANALYZE DATA = DIFF;
BY VISIT TIME TREATMENT;
MODELEFFECTS ESTIMATE;
STDERR STDERR;
RUN;
```

where the statement WHERE _TREATMENT=2 identifies the differences for active minus vehicle. The detailed code will be determined based on the final data.

Least squares means (LS Means) for each treatment, LS Means treatment differences and corresponding 95% CIs as estimated by the ANCOVA model will be provided.

In addition, ANCOVA models accounting for repeated measures will be run at Visit 6b as another supportive analysis. This ANCOVA model will include the time appropriate post-CAC itching scores at Visit 4a as a covariate and treatment group and time point as factors. The LS Means for each treatment, the LS Means treatment difference between OTX-DP and PV, and the corresponding 95% CIs will be calculated from these ANCOVA models. SAS pseudo-code for the ANCOVA model accounting for repeated measures at Visit 6 for multiply imputed data follows (Note: the same imputation routine described above [PROC MI \rightarrow PROC MIXED \rightarrow PROC MIANALYZE] will be employed using the below PROC MIXED pseudo-code):

```
PROC MIXED DATA=INDATA;
BY VISIT _IMPUTATION_;
CLASS SUBJID TREATMENT TIME;
MODEL SCORE = TREATMENT TIME BASELINE;
REPEATED TIME / SUBJECT=SUBJID TYPE=UN;
LSMEANS TREATMENT / PDIFF CL;
RUN;
```

where *INDATA* is the name of the input dataset sorted by *VISIT*, *_IMPUTATION_*, *SUBJID* and *TIME*.

An unstructured variance-covariance matrix will be used for the above repeated measures model. If the model does not converge using the unstructured matrix, the first order autoregressive structure and the compound symmetry structure will be employed, in that order.

Two-sample *t*-tests will also be used as unadjusted sensitivity analyses at each post-CAC time point, as well as non-parametric Wilcoxon rank sum tests for comparing OTX-DP and PV. Mean treatment differences, 95% CIs for each of the means, and 95% CIs for the mean differences will be presented for each post-CAC time point.

The following SAS code will be used for the t-test:

```
PROC TTEST DATA=INDATA;
BY VISIT TIME _IMPUTATION_;
CLASS TREATMENT;
VAR SCORE;
ODS OUTPUT STATISTICS = OUTPUTDF;
RUN;
PROC MIANALYZE DATA = OUTPUTDF;
BY VISIT TIME CLASS;
MODELEFFECTS MEAN;
STDERR STDERR;
RUN;
```

The following SAS code will be used for the Wilcoxon rank sum test:

```
ODS OUTPUT WILCOXONSCORES = WILCOXON (WHERE=(CLASS=:"1"));
PROC NPAR1WAY DATA = INDATA WILCOXON;
    BY VISIT TIME IMPUTATION ;
    CLASS TREATMENT;
    VAR SCORE;
RUN;
DATA WILCOXON;
  SET WILCOXON;
  BY VISIT TIME;
  MEAN = (SUMOFSCORES - EXPECTEDSUM) /N;
  STDERR = STDDEVOFSUM/N;
RUN;
PROC MIANALYZE DATA = WILCOXON ALPHA = 0.05;
BY VISIT TIME;
MODELEFFECTS MEAN;
STDERR STDERR;
RUN;
```

The ordering of the above code should be adjusted accordingly for the real data, to make sure the tests are performed to compare the treatment group vs. the placebo group.

Sensitivity or supportive analyses will be performed on the ITT population using LOCF, BOCF, and WCO imputations as well as observed data only (see Section 8.2.1 for additional data imputation details). The primary analysis will also be repeated on the PP population with observed data only.

A line graph will be produced to show mean (+/- standard error [SE]) ocular itching score by treatment group (OTX-DP, PV), visit (Visit 6b, Visit 8b), and time point (3, 5, and 7 minutes post-CAC). Mean change from baseline (+/- SE) for each treatment arm will be presented in a similar figure. Both figures will be presented separately for the ITT population using observed data only.

A listing of ocular itching scores for all subjects will also be provided.

